9.3 Variables

COVID-19 VACCINATION SCHEDULES

The nationwide registers provide full information on vaccination status including data on specific vaccine brand and date of administration. We will compare the specific heterologous and homologous (2-dose) primary- and (3-dose) booster vaccination schedules according to the study objectives. The date of the respective 2. or 3. vaccine dose examined will serve as the index date. The table below presents the intended vaccine schedules to be studied and comparison schedules.

		Co	ompariso	on vaccir	nation sc	hedules	(referen	ce)	
								Boo	ster
			Prim	nary sch	edules			schedules Homologous	
	Н	omologo	ous		Hetero	ologous			
Vaccination	AZD1	BNT1	MOD1	AZD1	AZD1	BNT1	MOD1	BNT1	MOD1
schedules (studied	AZD2	BNT2	MOD2	BNT2	MOD2	MOD2	BNT2	BNT2	MOD2
schedules)								BNT3	MOD3
Heterologous									
primary schedules									
AZD1BNT2		X							
AZD1MOD2			X						
BNT1MOD2		X							
MOD1BNT2		X							
Heterologous									
booster schedules									
AZD1AZD2BNT3	X							X	
AZD1AZD2MOD3	X								X
AZD1BNT2BNT3				X				X	
AZD1MOD2MOD3					X				X
BNT1BNT2MOD3		X						X	
MOD1MOD2BNT3			X					X	
BNT1MOD2MOD3						X		X	
MOD1BNT2BNT3							X	X	
BNT1MOD2BNT3					1	X		X	
MOD1BNT2MOD3							X	X	

Homologous booster							
schedules							
BNT1BNT2BNT3	X						
MOD1MOD2MOD3		X					
AZD, AZD1222; BNT, BNT162b2; M received as 1st, 2nd and 3rd dose.			s numbered	1 to 3 reflec	t the respec	tive vaccin	es

Colors indicate the variant that the specific studied vaccination schedule will primarily have provided protection against in the general population (i.e. not subpopulations targeted for priority vaccination such as frontline personnel, the elderly and individuals at risk of severe covid-19).

For objective #1 (VE of heterologous primary and booster vaccination compared to the homologous counterpart [i.e. 2-dose vs. 2-dose and 3-dose vs. 3-dose]), the expected largersized homologous mRNA vaccinated group will be the comparison schedule. For objective #2 (VE of heterologous and homologous booster vaccination compared to the counterpart primary vaccine schedules [i.e. 3-dose vs. 2-dose]), the comparison schedule will be the equivalent primary vaccine schedules to the two first doses received of the distinct studied booster schedule. By the intended comparisons presented above, the study will provide a comprehensive overview of the comparative VE of the majority of schedules used in the Nordic countries.

OUTCOMES

The endpoints will be: 1) a positive PCR test for SARS-CoV-2 (i.e. infection), 2) a covid-19 hospitalization, 3) covid-19 hospitalization at an intensive care unit (ICU) and 4) covid-19 related death. In the primary analyses we will follow up for the endpoints from start of follow-up defined as day 14 after the index date, and until 75 days have elapsed since the start of follow-up. These outcome ascertainment periods have been chosen to balance: a) that the follow-up among the comparison groups will be homogenous in contrast to longer periods of outcome ascertainment where right censoring at study end or another dose may differ substantially between comparison groups, and b) that we need to have sufficient follow-up for the assessment of hospitalization and mortality. When evaluating waning of immunity, follow-up for endpoints will continue beyond day 75.

Covid-19 hospitalization

Covid-19 hospitalization will be defined as an event fulfilling the following criteria: a) hospitalization with a PCR positive test for SARS-CoV-2 dated in the time period beginning 14 days before admission (day -14; the day of admission is day 0) and up to and including 2 days

after admission (day 2), b) inpatient hospital contact or a hospital contact with a duration of at least 12 hours and c) a covid-19 relevant diagnosis code (ICD-10: B342, B342A, B948A, B972, B972A, B972B, B972B1 or Z038PA1 – subject to country-specific coding practices, see table below - TIME-VARYING VARIABLES). Thus, individuals who are hospitalized for conditions not related to covid-19, but who coincidentally test positive in the period around admission (14 days before to 2 days after admission) will be included as an endpoint 1 (infection) but not an endpoint 2 (hospitalization). An example of this could be a patient with a fracture who test positive at admission as part of routine testing. This distinction is particularly important to make during periods of high incidence of infection as in the period of omicron. Covid-19 hospitalization to an ICU (endpoint 3) will be assessed among those individuals fulfilling the criteria for covid-19 hospitalization (endpoint 2).

Covid-19 related mortality

Covid-19 related death will be defined as death within 30 days after PCR positive test for SARS-CoV-2. While this definition will allow us to assess the outcome contemporarily (i.e. no lag time) and is an epidemiological standard measure of infection-related mortality, a limitation to this approach is that it does not include covid-19 related death later than 30 days and may include deaths not specifically related to severe covid-19. Potential bias from these limitations, however, are mitigated by use of the comparative design (in which, we would not expect the risk of potential misclassification to be different between comparative groups). Some countries may be able to supplement with information from cause-of-death registers, but the inclusion of this information will be subject to availability.

In secondary analyses, all outcomes will be sub classified according to SARS-CoV-2 variants of concern using either a "periods of dominance"-approach where for each country we have identified the periods where specific variants dominated or, subject to data availability, variant-PCR and WGS results – see subsection *Intended additional analyses* below.

Through use of the planned outcomes, we will be able to provide information on the VE in relation to any SARS-CoV-2 infection as well as severe covid-19. In addition, variant-specific secondary analyses will provide information on VE according to specific variants of concern. The Nordic health care registers do not hold information to distinguish between symptomatic and asymptomatic documented SARS-CoV-2 infection.

COVARIATES

We will take the following potential confounders into account: age (using year of birth), sex, calendar month (of vaccination; ie, the index date) and vaccination priority group (nursing

home residents, healthcare personnel and individuals at risk of severe covid-19 due to comorbidities).

To account for the risk of severe covid-19, we will adjust for vaccine priority groups; specifically established for each country. In Denmark, the covid-19 vaccine priority groups were governmentally assigned and individuals were prioritized according to the risk of severe infection as well as whether being health and social care workers. In the remaining countries, vulnerable individuals (such as those receiving nursing care or living in nursing homes) and healthcare personnel will be identified. Further, we will also include comorbidities that are related to the risk of severe covid-19 as separate covariates in our adjustment model (see table of included variables below). The selected ICD-10 codes defining the comorbidities are country-specific and have been chosen for general surveillance purposes based on inputs from national experts and country-specific registration practices. In the interest of saving time on developing a common set of diagnoses codes, we have chosen to take advantage of these coding schemes. In addition, country-specific codes may even be better at identifying comorbidity-related risk groups within each country than common codes.

VARIABLE	COUNTRY	DATA SOURCE AND DETAILS	VALUES/CODES
Age	Denmark	The Civil Registration System. Defined as age at first covid-19 vaccination	
	Finland	The Finnish Population Information System. Defined as age at first covid-19 vaccination.	Categorical: 5-year bins; and 18-40 years 40-59, 60-74, and 75- for stratified analyses
	Norway	Norwegian Population Register. Defined as age at first covid-19 vaccination.	of age-specific comparisons.
	Sweden	The Total Population Register. Defined as age at first covid-19 vaccination.	

The intended included variables and the country-specific data sources, definition details and values are presented in the table below.

	Denmark	The Civil Registration System. Defined as biological sex.	
Sex	Finland	The Finnish Population Information System. Defined as biological sex.	Binary: male, female
	Norway	Norwegian Population Register. Defined as biological sex.	
	Sweden	The Total Population Register. Defined as biological sex.	
	Denmark	The Civil Registration System. Defined as known national resident.	
Desidence	Finland	Not available.	
Residency (citizenship)	Norway	Norwegian Population Register. Defined as known national resident.	Binary: yes/no
	Sweden	The Total Population Register. Defined as known national resident.	
	Denmark	The Danish Vaccination Register. Defined by the date where the respective vaccine dose examined was administered (i.e. 2nd or 3rd dose) and grouped into monthly intervals according to months since start of study period.	
Calendar month	Finland	The National Vaccination Register. Defined by the date where the respective vaccine dose examined was administered (i.e. 2nd or 3rd dose) and grouped into monthly intervals according to months since start of study period.	Categorical (14 levels): calendar month 1 (27 December 2020 to 31 January 2021) to month 14 (February 2022)
	Norway	The Norwegian Immunisation Register (SYSVAK). Defined by the date where the respective vaccine dose examined was administered (i.e. 2nd or 3rd dose) and	

		grouped into monthly intervals according to months since start of study period. The National Vaccination Register. Defined by the date where the respective	
	Sweden	vaccine dose examined was administered (i.e. 2nd or 3rd dose) and grouped into monthly intervals according to months since start of study period.	
	Denmark	The Danish Vaccination Register. Defined as governmentally assigned covid-19 vaccine priority groups, prioritized according to the risk of severe infection as well as whether being health and social care workers (assigned before first covid-19 vaccination).	Categorical (4 levels): Target risk groups, healthcare personnel, selected relatives of people at high risk, others
Covid-19 vaccine priority groups	Finland	Register of Social Assistance. Vulnerable individuals defined as individuals in 24-hours care (binary status per 27 December 2020). Social and Healthcare Professionals Register. Healthcare personnel defined as individuals with the right to act as health care personnel.	Categorical (3 levels): Vulnerable individuals, healthcare personnel, others
	Norway	The Norwegian Information System for the Nursing and Care Sector. Vulnerable individuals defined as nursing home resident (binary status per 27 December 2020). State register of employers and employees. Healthcare personnel defined as binary status per 27 December 2020.	Categorical (3 levels): Vulnerable individuals, healthcare personnel, others
	Sweden	Register on persons in nursing homes.	Categorical (3 levels): Vulnerable individuals,

		Vulnerable individuals defined as nursing home resident (binary status as of December 2020) The Longitudinal integrated database for health insurance and labour market studies. Healthcare personnel defined as healthcare worker occupation status as of October 2018 (binary).	healthcare personnel, others
Comorbidity 1: Chronic pulmonary disease (CPD)	Denmark	The National Patient Register. Defined as primary diagnoses regardless of type of hospital contact registered before first covid-19 vaccination (look- back 3 years).	Binary: yes/no ICD-10 codes: J40-J47, J60–J67, J68.4, J70.1, J70.3, J84.1, J92.0, J96.1, J98.2, J98.3
Comorbidity 1: CPD	Finland	Care register for Health Care and Register of Primary Health Care Visits. Defined as primary or secondary diagnoses before 27 December 2020 (look-back 3 years).	Binary: yes/no ICD-10 codes: J41-J47 ICPC-2: R96
Comorbidity 1: CPD	Norway	Norwegian Patient Register. Defined as any recorded ICD-10 diagnosis during inpatient or outpatient contact in hospital or from private- practicing specialists and before first covid-19 vaccination (look-back 3 years).	Binary: yes/no ICD-10 codes: E84, J41-J47, J701, J703, J84, J98
Comorbidity 1: CPD	Sweden	National Patient Register. Defined as any recorded ICD-10 diagnosis during inpatient or outpatient contact and before first covid- 19 vaccination (look-back 3 years).	Binary: yes/no ICD-10 codes: E84, J41-J47 J84, J98
Comorbidity 2:	Denmark	The National Patient Register.	Binary: yes/no

[
Cardiovascular conditions and diabetes (CVD/DM)		Defined as primary diagnoses regardless of type of hospital contact registered before first covid-19 vaccination (look- back 3 years).	ICD-10 codes: E10- E11, I11.0, I13.0, I13.2, I20-I23, I42.0, I42.6-I42.9, I48, I50.0- I50.3, I50.8, I50.9
Comorbidity 2: CVD/DM	Finland	Care register for Health Care, Register of Primary Health Care Visits, Special Reimbursement Register and Prescription Centre database. Defined as primary or secondary diagnoses or drug prescriptions before 27 December 2020 (look-back 3 years).	Binary: yes/no ICD-10 codes: E10, E11, E13, E14, I11– I13, I15, I20–I25, I50 ICPC-2 codes: T90, T89 ATC codes:A10A, A10B
Comorbidity 2: CVD/DM	Norway	Norwegian Patient Register. Defined as any recorded ICD-10 diagnosis during inpatient or outpatient contact in hospital or from private- practicing specialists and before first covid-19 vaccination (look-back 3 years).	Binary: yes/no ICD-10 codes: E10-E14 I05-I09, I110, I130, I132, I1420, I20-I23, I25-I28, I33-I39, I426- I429, I48, I50
Comorbidity 2: CVD/DM	Sweden	National Patient Register. Defined as any recorded ICD-10 diagnosis during inpatient or outpatient contact and before first covid-19 vaccination (look-back 3 years). Swedish Prescribed Drug Register. Antidiabetic drugs use defined as ≥2 filled prescriptions during 2020.	Binary: yes/no ICD-10 codes: E10- E14, I05-I09, I110, I2, I34-I37, I39, I42, I43, I46, I48-I50 ATC code: A10
Comorbidity 3: Autoimmunity related conditions (AIC) ^a	Denmark	The National Patient Register. Defined as primary diagnoses regardless of type of hospital contact registered before first covid-19 vaccination (look- back 3 years).	Binary: yes/no ICD-10 codes: D51.0, D59.0, D59.1, D69.0, D69.3, D86, E05.0, E06.3, E27.1, E27.2, G12.2G, G35, G61.0, G70.0, I00, I01, K50, K51, K74.3, K90.0, L12, L40, L52,

			L80, L93, M05, M06, M08, M30.0, M31.3, M31.5, M31.6, M32, M33, M34, M35, M45
Comorbidity 3: AIC ^a	Finland	Care register for Health Care, Special Reimbursement Register and Prescription Centre database. Defined as primary or secondary diagnoses or drug prescriptions before 27 December 2020 (look-back 3 years).	Binary: yes/no ICD-10 codes: D70.81, D70.89, D80–D84, E31.00, E25.0, E27.1, E27.2, E27.4, E31.00, E31.01, E31.08, E89.6, D86, K50, K51, L40, M02, M05–M07, M13.9, M45, M46.0, M46.1, M46.9, M94.1 ATC-codes: H02AB02, H02AB04, H02AB06, H02AB07, L01BA01, L01XC02, L04AA06, L04AA10, L04AA13, L04AA18, L04AA24, L04AA26, L04AA29, L04AA33, L04AA37, L04AB, L04AC, L04AD01, L04AX03
Comorbidity 3: AICª	Norway	Norwegian Patient Register. Defined as any recorded ICD-10 diagnosis during inpatient or outpatient contact in hospital or from private- practicing specialists and before first covid-19 vaccination (look-back 3 years).	Binary: yes/no ICD-10 codes: G35, K50-K51, M05-M09, M13-M14
Comorbidity 3: AICª	Sweden	National Patient Register. Defined as any recorded ICD-10 diagnosis during inpatient or outpatient	Binary: yes/no

		contact and before first covid-19 vaccination (look-back 3 years).	ICD-10 codes: D86, G35, K50, K51, L40, M05-M09, M13, M14, M45
Comorbidity 4: Cancer	Denmark	The National Patient Register. Defined as primary diagnoses regardless of type of hospital contact registered before first covid-19 vaccination (look- back 3 years).	Binary: yes/no ICD-10 codes: C00- C85 (without C44), C88, C90-C96
Comorbidity 4: Cancer	Finland	Care register for Health Care and Special Reimbursement Register. Defined as primary or secondary diagnoses before 27 December 2020 (look-back 3 years).	Binary: yes/no ICD-10 codes: C00- C97 (without C44), D051, D39
Comorbidity 4: Cancer	Norway	Norwegian Patient Register. Defined as any recorded ICD-10 diagnosis during inpatient or outpatient contact in hospital or from private- practicing specialists and before first covid-19 vaccination (look-back 3 years).	Binary: yes/no ICD-10 codes: C00-C96 (without C44)
Comorbidity 4: Cancer	Sweden	National Patient Register. Defined as any recorded ICD-10 diagnosis during inpatient or outpatient contact and before first covid-19 vaccination (look-back 3 years).	Binary: yes/no ICD-10 codes: C00-C96 (without C44), D45- D47
Comorbidity 5: Moderate to severe renal disease (CKD)	Denmark	The National Patient Register. Defined as primary diagnoses regardless of type of hospital contact registered before first covid-19 vaccination (look- back 3 years).	Binary: yes/no ICD-10 codes: I12, I13, N00-N05, N07, N11, N14, N17-N19, Q61
Comorbidity 5: CKD	Finland	Care register for Health Care and Special Reimbursement Register. Defined as primary or secondary diagnoses before 27 December 2020 (look-back 3 years).	Binary: yes/no ICD-10 codes: I12, I13, N00-N05, N07, N08,

			N11, N14, N18, N19, E10.2, E11.2, E14.2
Comorbidity 5: CKD	Norway	Norwegian Patient Register. Defined as any recorded ICD-10 diagnosis during inpatient or outpatient contact in hospital or from private- practicing specialists and before first covid-19 vaccination (look-back 3 years).	Binary: yes/no ICD-10 codes: I12-I13, N00-N05, N07, N11, N14, N17-N19, Q61
Comorbidity 5: CKD	Sweden	National Patient Register. Defined as any recorded ICD-10 diagnosis during inpatient or outpatient contact and before first covid-19 vaccination (look-back 3 years).	Binary: yes/no ICD-10 codes: I12, I13, N00-N05, N07, N11, N14, N17-N19, Q61

TIME-VARYING VARIABLES

VARIABLE	COUNTRY	DATA SOURCE AND DETAILS	VALUES
Vaccination status	Denmark	The Danish Vaccination Register. Defined according to the specific administered covid-19 vaccines and date of vaccinations.	Categorical (multiple levels): AZD1, AZD1AZD2,
	Finland	The National Vaccination Register. Defined according to the specific administered covid-19 vaccines and date of vaccinations.	
	Norway	The Norwegian Immunisation Register (SYSVAK). Defined according to the specific administered covid-19 vaccines and date of vaccinations.	AZD1MOD2, BNT1BNT2, BNT1, BNT2MOD3 etc.
	Sweden	The National Vaccination Register. Defined according to the specific administered covid-19 vaccines and date of vaccinations.	
	Denmark	The Danish Microbiology Database.	Binary: yes/no

Documented SARS CoV-2 infection	Finland Norway	Defined as the date of registered positive PCR test for SARS CoV-2. National Infectious Diseases Register. Defined as the date of registered positive PCR test for SARS CoV-2. Norwegian Surveillance System for Communicable Diseases (MSIS). Defined as the date of registered positive PCR test for SARS CoV-2.	
	Sweden	Register on surveillance of notifiable communicable diseases (SmiNet). Defined as the date of registered positive PCR test for SARS CoV-2.	
	Denmark	The National Patient Register and the Danish Microbiology Database. Defined as hospitalization on the day of, within 14 days of or in the two days after a PCR positive test for SARS-CoV-2, b) inpatient contact or at least 12 hours of contact, c) a covid-19 relevant diagnosis code (ICD-10: B342, B342A, B948A, B972, B972A, B972B, B972B1, Z038PA1)	
Hospitalization for covid-19	Finland	National Care Register for Health Care and the National Infectious Diseases Register. Defined as hospitalization on the day of, within 14 days of or in the two days after a PCR positive test for SARS-CoV-2, b) inpatient hospital contact, and c) main diagnosis starting with one of the following J0, J1, J20, J21, J22, J46, J80, J81, J82, J83, J84, J851, J86, U071, U072).	Binary: yes/no
	Norway	The Norwegian Patient Registry and the Norwegian Surveillance System for Communicable Diseases (MSIS).	

		Defined as hospitalization on the day of, within 14 days of or in the two days after a PCR positive test for SARS-CoV-2, b) inpatient contact or at least 12 hours of contact, c) a covid-19 relevant diagnosis code (ICD-10: B342, B342A, B948A, B972, B972A, B972B, B972B1, Z038PA1)	
	Sweden	The Swedish Patient Register and the Register on surveillance of notifiable communicable diseases (SmiNet). Defined as hospitalization on the day of, within 14 days of or in the two days after a PCR positive test for SARS-CoV-2, b) inpatient contact or at least 12 hours of contact, c) a covid-19 relevant diagnosis code (ICD-10: U071, U072, U109)	
	Denmark	The National Patient Register and the Danish Microbiology Database. Defined as admission to an intensive care unit facility during hospitalization for covid-19.	
Intensive care unit admission	Finland	Finnish Intensive Care Consortium's Quality Register for Intensive Care, National Care Register for Health Care and the National Infectious Diseases Register. Defined as admission to an intensive care unit facility during hospitalization for covid-19.	Binary: yes/no
	Norway	The Norwegian Patient Registry (NPR) and the Norwegian Surveillance System for Communicable Diseases (MSIS). Defined as admission to an intensive care unit facility during hospitalization for covid-19.	

	Sweden	The Swedish Patient Register and the Register on surveillance of notifiable communicable diseases (SmiNet). Defined as admission to an intensive care unit facility during hospitalization for covid-19.	
Covid-19 death	Denmark	The Civil Registration System and the Danish Microbiology Database. Defined as (the date of) death within 30 days after PCR positive test for SARS- CoV-2.	
	Finland	The Finnish Population Information System and the National Infectious Diseases Register. Defined as (the date of) death within 30 days after PCR positive test for SARS- CoV-2.	
	Norway	Norwegian Population Register and the Norwegian Surveillance System for Communicable Diseases (MSIS). Defined as (the date of) death within 30 days after PCR positive test for SARS- CoV-2.	Binary: yes/no
	Sweden	The Total Population Register and the Swedish Patient Register and the Register on surveillance of notifiable communicable diseases (SmiNet). Defined as (the date of) death within 30 days after PCR positive test for SARS- CoV-2. Possible to asses cause-of-death using ICD-10 coding of U071, U072, U109.	

^aAutoimmunity related conditions (AIC) includes diagnoses of disorders such as inflammatory bowel diseases, diseases involving the blood, immune mechanism or endocrine systems, inflammatory rheumatic diseases, psoriasis, lupus erythematosus, multiple sclerosis; subject to country-specific definitions.

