The Norwegian Information System for the Nursing and Care Sector (IPLOS) (36)	The register holds information on the health care services that are provided by municipalities in Norway. Report of applicants and recipients of such services to the register is mandatory for all municipalities. The register includes information on home care service and out-of-hospital institutional care, including short- and long-term nursing home stay.
The Norwegian Immunisation Register (SYSVAK) (37)	The register holds information of administered vaccines in Norwegian vaccination programs, including the date of administration and type of vaccine. For the covid-19 vaccines, reporting to the register have been mandatory.
Norwegian Surveillance System for Communicable Diseases (MSIS)	The register holds information on selected infectious diseases for which reporting to the register is mandatory. This includes all covid-19 tests and the date of testing and test results.
The Norwegian Patient Registry (NPR) (38)	The register holds information on all contacts with specialist health-care services in Norway, including admission and discharge dates as well as diagnoses (recorded according to ICD-10) during hospitalization or outpatient contact.
SWEDEN	
The Total Population Register (39)	The register contains information on the unique personal identifier for all individuals in Sweden as well as general demographic information such as date of birth, sex, country of birth, place of residence, date of immigration and emigration and date of death. The register is held by Statistics Sweden.
The Longitudinal Integrated Database For Health Insurance And Labour Market Studies (LISA) (40)	The database contains a wide range of socioeconomic information including occupation (such as healthcare worker). The register is held by Statistics Sweden.
Register On Persons In Nursing Homes (41)	The register holds information on nursing care given to elderly and/or persons with physical, psychiatric or intellectual disabilities at either nursing homes, own homes or other institutions. The register is held by the National Board of Health and Welfare.
The National Vaccination Register (42)	The register contains information on administered covid-19 vaccines including data on date of administration, the specific vaccine products,

	substance, formulation, batch number and dose number (for repeated doses) since 1 January 2021. The register is held by the Public Health Agency of Sweden.

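### In Finland, Norway and Sweden the vulnerable level omits people cared for at home, though the protocol's text and registers reach them, so avoidable residual frailty confounding is possible

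*Protocol*

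**What the plan says.** Section 9.3 (Covariates) adjusts for vaccine priority group in order to account for the risk of severe covid-19. For Finland, Norway and Sweden it says: "In the remaining countries, vulnerable individuals (such as those receiving nursing care or living in nursing homes) and healthcare personnel will be identified". The list of confounders just before that passage mentions nursing home residents only.

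The variable table in the same section gives the operational definitions:

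- Finland: "Vulnerable individuals defined as individuals in 24-hours care (binary status per 27 December 2020".
- Norway: "Vulnerable individuals defined as nursing home resident (binary status per 27 December 2020".
- Sweden: "Vulnerable individuals defined as nursing home resident (binary status as of December 2020".

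The variable is coded as "Categorical (3 levels): Vulnerable individuals, healthcare personnel, others" in these three countries. Denmark uses government-assigned groups with four levels.

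Section 9.4 describes what the source registers contain. For the Norwegian care register (IPLOS): "The register includes information on home care service and out-of-hospital institutional care, including short- and long-term nursing home stay". The Swedish register on persons in nursing homes covers "nursing care given to elderly and/or persons with physical, psychiatric or intellectual disabilities at either nursing homes, own homes or other institutions". The Finnish Register of Social Assistance is described as covering long-term care and social assistance, which may be given in people's own homes as well as in institutions.

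Under Section 9.7 the priority group enters the logistic model for the objective 1 weights and the propensity score for objective 2 matching.

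**The concern.** Care dependence is a marker of frailty, and frailty raises the risk of hospitalization and death. It may also affect when a person receives a dose. Section 9.2 itself says that current illness can delay vaccination appointments. It says so about unvaccinated comparators, but the same reasoning could apply to objective 2 controls, who on the index date have not yet had a third dose.

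If home-care recipients sit in *others*, no covariate identifies them directly. Any imbalance between schedules that age, sex, calendar month and comorbidity do not remove would pass into the severe-outcome estimates for three of the four countries, and from there into the pooled estimates. The death endpoint is particularly exposed. It counts any death within 30 days of a positive test, and the protocol accepts that some of these deaths may not be due to covid-19.

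Objective 1 asks whether heterologous schedules are non-inferior, so even a modest distortion could matter there. Section 9.9 does not list residual confounding by frailty among the limitations.

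**Working it through.** **1. Definitions side by side**

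| Country | Text of 9.3 | Variable table in 9.3 | Register content in 9.4 |
|---|---|---|---|
| Finland | nursing care or nursing home | 24-hour care | assistance, including in own homes |
| Norway | nursing care or nursing home | nursing-home resident | home care service and institutional care |
| Sweden | nursing care or nursing home | nursing-home resident | nursing care in nursing homes, own homes, other institutions |

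The text names two example groups and the table keeps only the residential one. With three levels, a home-care recipient who is not healthcare personnel can only be *others*. The restriction is a choice of definition. As described, the registers in Norway and Sweden would allow the wider one.

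**2. Do other covariates fill the gap?** The five comorbidity flags are lung disease, cardiovascular disease or diabetes, autoimmune conditions, cancer and renal disease. None records functional status or receipt of care. Month of dose 2 is a partial proxy, because Section 9.7 says its timing is highly correlated with risk of severe covid-19, and objective 2 matches on it. In the 3-dose versus 3-dose comparisons of objective 1, the month adjusted for is that of dose 3, so that proxy is absent.

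**3. Possible size.** The protocol gives no figure to reproduce: no home-care share, no imbalance between schedules and no associated risk. All inputs below are assumptions. For one unmeasured binary confounder the factor by which the risk ratio (RR) is off is

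B = [1 + p1(k − 1)] / [1 + p0(k − 1)],

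where p1 and p0 are the home-care shares in the studied and comparison schedules that remain after adjustment, and k is the risk ratio of home care for the severe outcome.

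| p0 | p1 | k | B | reversed (1/B) |
|---|---|---|---|---|
| any | = p0 | any | 1.00 | 1.00 |
| 0.15 | 0.18 | 2 | 1.18/1.15 = 1.026 | 0.975 |
| 0.10 | 0.15 | 3 | 1.30/1.20 = 1.083 | 0.923 |
| 0.10 | 0.20 | 4 | 1.60/1.30 = 1.231 | 0.812 |

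Smaller shares give smaller factors. At 2% versus 3%, B is 1.03/1.02 = 1.010 for k = 2 and 1.12/1.08 = 1.037 for k = 5. A harsher case, 10% versus 20% with k = 5, gives 1.80/1.40 = 1.286.

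**4. What the range means for the estimates.** At the largest factor in the table, a true RR of 1.00 would read 1.23 or 0.81. For an assumed true effectiveness of 80% (RR 0.20), it would read 1 − 0.20 × 1.231 = 75%, or 1 − 0.20/1.231 = 84%.

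**5. A consequence that needs no imbalance.** The example results table in Section 12 has rows for vulnerable/high-risk individuals, healthcare workers and others. In three countries home-care recipients will be reported in the last row. Denmark's groups are defined differently, so the pooled rows mix definitions.

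**The case against.** The contradiction is mild. The sentence in 9.3 uses *such as*, so it gives examples, and the section refers the reader to the table for definition details. The earlier list of confounders agrees with the table for Norway and Sweden, and the groups are said to be set country by country. The variable is a priority group, not a frailty index. All of this is fair, but the table still drops one of the two groups that the text names.

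A reader might infer that the severe-outcome risk ratios are confounded by frailty. The documents do not support that. It would require home-care status to differ between two vaccinated schedules within levels of age, sex, month, comorbidity and priority group, and nothing in the protocol shows this. Nor does the protocol describe any route by which home care determines vaccine brand.

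It would also be wrong to say that the design does nothing. Objective 1 restricts comparators to the age and calendar window holding 95% of the heterologous group and then weights on 5-year age, month, sex, comorbidity and priority group. Objective 2 matches on age and month of dose 2. In Norway AZD1222 went to frontline personnel (Section 9.5), so AZD-primed comparisons there should contain few elderly home-care recipients.

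Register support is uneven. The Finnish description mentions assistance in own homes but does not name home care or home nursing. The protocol does not show that home-care status is dated, complete or comparable across countries. These points limit the conclusion, but they do not remove the gap in the covariate.

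**Conclusion.** The point holds as a gap between text and variable that leaves avoidable residual frailty confounding possible for hospitalization, ICU admission and death in Finland, Norway and Sweden, mainly in older strata. Neither its direction nor its size can be fixed from the protocol. The factor is 1.00 if home care is balanced after adjustment. It is about 1.03 to 1.23 in either direction under assumed residual imbalances of 3 to 10 points and a 2- to 4-fold risk.

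The range of 0.81 to 1.23 around a true risk ratio of 1.00 should not be read as an expected error. Its extremes need home care to be twice as common in one arm after adjustment, together with a 4-fold risk. The assumed shares describe older people and do not carry over to the whole adult cohort. The case for change rests on the low cost of the remedy, not on demonstrated bias.

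**What to change.** - Reconcile the list of confounders, the text and the variable table in Section 9.3, so that they define the vulnerable group in the same way for Finland, Norway and Sweden.
- Add a baseline level *receives home care or home nursing*, taken from the registers already named: IPLOS, the Swedish care register and, where it identifies such care, the Finnish Register of Social Assistance.
- Use this level in the objective 1 weight model and the objective 2 propensity score.
- State in Section 12 how the level maps to the priority-group rows of the results tables.

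The cost is one extra category to derive, some differences in definition between countries, and a small change to the priority-group rows. No exact-match variable changes, because priority group enters the matching only through the propensity score.
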